### ***Outcomes***

The primary outcome will be the occurrence of symptomatic UTI within the 6 month treatment period. Clean catch urine culture will be collected whenever subjects report symptoms of a UTI: fever (>38 degrees C), urgency, frequency, dysuria or suprapubic tenderness. Standing orders for urine analysis and culture will be present at the local institution's lab and women will be asked to have all urine labs done at the parent site as per standard clinical practice. If subjects are not able to submit a specimen to the local site, lab orders will be faxed to a local laboratory for collection and results sent to parent institution as per clinical care standards. Treatment will be up to the discretion of the treating physician. If they are unable to perform a clean catch, they may come in to the office for a catheterized specimen according to the treating physician's clinical recommendations. As these cultures would be obtained regardless of study participation, they will be obtained and billed according to standard of care. The presence of a UTI in the 6 month window will be the primary outcome of the study, but secondarily we will assess the rate of UTIs over the course of the year that occur in order to assess efficacy.

Other secondary outcomes include QOL questionnaires mentioned above. These will help us to look at changes in general QOL, as well as irritative bladder symptoms and sexual function, impacted by study drug. Adherence will also be assessed. We will weigh tubes of cream to determine adherence with creams, as well as collect medication diaries (adherence will be defined as  $\geq 80\%$  use as measured by weight of the vaginal cream tubes). For the ring, compliance will be assessed based on presence of the ring vaginally at 3 month visits.

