### ***Analysis***

#### ***Sample Size Consideration***

The primary outcome is whether there is any occurrence of symptomatic UTI at the end of the randomized

treatment period. Based on the literature [15] we assume that the rate of at least one UTI in the placebo group is 63%. With 20 subjects at the end of the randomized treatment period in each of the two treatment groups, we will have 80% power to detect a difference using Fisher's exact test if the corresponding rate in an active treatment group is 16% [15] under a two-sided significance level of 0.05. A total sample size of 48 (24 subjects per group) will be needed allowing for 20% attrition seen to date in the study.

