#### *Data Analysis*

Subject characteristics including baseline measures will be compared across the randomized groups using t-test or chi-squared test (or their nonparametric / small sample counterparts) as appropriate, and will be adjusted in a regression model in addition to the primary comparisons above. It is known that even if the characteristics are balanced across the groups, such adjust can improve the efficiency of the comparisons [32]. For the secondary outcomes, frequencies (counts) of UTIs in the randomized period as well as the additional follow-up period will be compared between groups using a Poisson model; the QOL outcomes will be compared between groups using t-tests, and between baseline and 12 months within an active treatment group using paired t-test; adherence will be compared between the ring group and the active cream group as a dichotomous variable, with adherence for the latter group defined as  $\geq 80\%$ . While the primary comparisons are intent-to-treat, secondary comparisons will be carried out among those subjects who have adhered. In addition, for the variables that are collected at three or more time points, longitudinal data analysis will be performed using random effects models. As the attrition rate is expected to be as high as 20%, whether the missing data mechanism might be informative will be checking using methods such as those described by Ridout et al. [33] in case of informative (non-ignorable) missingness, sensitivity analysis will be carried out.

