## **10. HUMAN SUBJECTS**

Our total subject recruitment will be 48 subjects (assuming 20% drop out). However, if we do not such a drop out rate, once we reach 40 subjects total who have completed 6 months (achievement of the primary outcome), we will stop study enrollment.

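### Sensitivity analysis for dropout depends on a check that cannot detect non-ignorable missingness; it should be unconditional for the primary outcome

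*Combined protocol and SAP*

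**What the plan says.** Under Data Analysis, the plan anticipates attrition of up to 20% and says that "whether the missing data mechanism might be informative will be checking using methods" of the kind in a cited paper, whose title in the bibliography concerns tests for random dropout in repeated measurements. It continues: "in case of informative (non-ignorable) missingness, sensitivity analysis will be carried out". It does not say what that sensitivity analysis would be. The same section sets the analysis principle: "While the primary comparisons are intent-to-treat, secondary comparisons will be carried out among those subjects who have adhered".

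The endpoint is binary. Under Outcomes: "The presence of a UTI in the 6 month window will be the primary outcome of the study". The sample size section allows for loss: "A total sample size of 48 (24 subjects per group) will be needed allowing for 20% attrition seen to date in the study". Section 10 closes recruitment earlier if loss is lower: "once we reach 40 subjects total who have completed 6 months (achievement of the primary outcome), we will stop study enrollment".

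Some outcomes can be recovered after a woman leaves. The Outcomes section has outside laboratory results sent to the parent site, and section 16 provides for authorization to collect UTIs and clinic visits.

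**The concern.** The plan makes sensitivity analysis the consequence of a positive finding. The finding it requires, that missingness is non-ignorable, concerns values nobody has seen. A dropout test answers a different question: whether leaving is related to what was recorded. A negative answer is compatible with any degree of dependence on the missing outcome, and in a trial this small a negative answer is likely even when recorded factors do matter.

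The branch most likely to be followed is thus the one in which the plan promises nothing. Readers would then not be assured of seeing how far the primary result depends on what happened to the women who left. If the effect is somewhat smaller than the design assumes, one or two of those women can decide significance.

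**Working it through.** **Inputs.** From Sample Size Consideration: 63% versus 16% with at least one UTI, Fisher's exact test, two-sided 0.05, 80% power, 20 evaluable and 24 enrolled per group. From section 10: 48 recruited, 40 completing. My assumptions: 4 women per arm (24 − 20) leave with no UTI recorded and unknown 6-month status, and completer counts are as stated below.

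**1. The plan's own figure.** The uncorrected two-proportion formula is n₀ = [1.96·√(2·0.395·0.605) + 0.842·√(0.63·0.37 + 0.16·0.84)]² / 0.47² = 15.75. The continuity correction gives n = (15.75/4)·[1 + √(1 + 4/(15.75·0.47))]² = 19.8, so 20 per group, as stated. Full enumeration of Fisher's test gives power of 82.3% at 20 per group. The sample size is not in question.

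**2. What a check can learn.** In an arm with 20 known outcomes and 4 unknown, the data fix the 20 and the number of blanks. The number of UTIs among the 4 could be 0, 1, 2, 3 or 4, and each value is equally compatible with the observed data. No test on those data can choose among them.

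**3. Power for what can be tested.** Expected dropouts are 48 − 40 = 8, against 40 completers. For a recorded binary factor present in 75% of dropouts and 37.5% of completers, Fisher's test has about 44% power. The effect size is assumed and the cited method is not a Fisher test, so this only indicates what 8 dropouts can support.

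**4. How far the unknown outcomes move the result.** Add i UTIs (0 to 4) to placebo and j (0 to 4) to estrogen, and recompute Fisher's two-sided p with 24 per arm.

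| Completers (placebo vs estrogen) | Completers only | All unknown UTI-free (i=0, j=0) | All unknown UTI (i=4, j=4) | Least favorable case that matters |
|---|---|---|---|---|
| 13/20 vs 3/20 | 0.003 | 13/24 vs 3/24: 0.005 | 17/24 vs 7/24: 0.009 | i=0, j=4, 13/24 vs 7/24: 0.14 |
| 12/20 vs 4/20 | 0.022 | 12/24 vs 4/24: 0.030 | 16/24 vs 8/24: 0.042 | i=0, j=1, 12/24 vs 5/24: 0.069 |

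For 13/20 versus 3/20, 3 of the 25 combinations reach p ≥ 0.05: (i, j) = (0, 3), (0, 4) and (1, 4). For 12/20 versus 4/20, 10 of 25 do.

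These counts are not probabilities. Weighting each combination binomially gives the chance of losing significance:

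- Dropouts follow the design rates (63% and 16%): 0.04% for 13/20 versus 3/20, and 3% for 12/20 versus 4/20.
- Dropouts have a 40% UTI risk in both arms (assumed): 3% and 36%.

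**The case against.** The plan does address missing data, names a method, and does not forbid sensitivity analysis after a negative check. At the design effect, treating both arms alike leaves the conclusion unchanged. Four unknowns per arm is an upper-end assumption: a UTI before dropout already meets the endpoint, and laboratory results and records may settle other cases. All of this stands and limits the size of the point. None of it makes the condition testable or commits the plan to an analysis.

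Several stronger readings are tempting, but the documents do not support them.

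- **That intent-to-treat conflicts with a completer analysis.** The sample size section counts women at the end of treatment ("With 20 subjects at the end of the randomized treatment period in each of the two treatment groups") and section 10 counts completers, but these set and stop recruitment. Neither defines an analysis set, and inflating for attrition is compatible with intent-to-treat.
- **That a rule could be chosen with outcomes in view.** Enrollment is complete and providers know the allocation. However, Overall Design also says that providers will be blinded to outcome measures, and the quarterly review in section 15 is described by subject, not by arm.
- **That the missing-data sentence covers only the repeated measures.** It follows the sentence "for the variables that are collected at three or more time points, longitudinal data analysis will be performed using random effects models", but it opens with attrition in the study as a whole and is not restricted to those variables.
- **That unequal loss between arms would cause large swings in power.** The documents give no dropout by arm for this trial. Such swings would come from an assumed split and would mostly be bias produced by the counting rule.

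**Conclusion.** The concern holds in a limited form. The condition on sensitivity analysis is unsound because observed data cannot establish it, and a negative check on about 8 dropouts is weak evidence even about recorded factors. The consequence is modest at the design effect, where significance is lost only at or near the worst case. It is material for a smaller effect: at 12/20 versus 4/20, one UTI among the estrogen dropouts and none among the placebo dropouts moves p from 0.030 to 0.069. These sizes rest on the assumed completer counts and on 4 unknown UTI-free losses per arm; fewer unknowns would narrow the range.

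As a secondary note, the plan does not write out how a woman who leaves UTI-free with unknown status is counted in the primary test. That is missing detail worth adding, not the defect described here.

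**What to change.** In Data Analysis, delete the condition and keep the dropout check as descriptive only. State that, for the binary primary outcome in all randomized women:

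- any qualifying UTI before dropout counts as an event;
- remaining 6-month status is first sought from the laboratory results and records the study already collects, within the authorization in section 16;
- a tipping-point table by arm, including best and worst case, is always reported over the possible outcomes of women whose status stays unknown.

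The primary counting rule for those women can be written in the same place.

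The cost is a few sentences, a record check for about 8 women if losses match the plan, and one small table. No visits or participants are added. The downside is that the result may look less robust than a single p-value suggests.

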## **10. HUMAN SUBJECTS**

Our total subject recruitment will be 48 subjects (assuming 20% drop out). However, if we do not such a drop out rate, once we reach 40 subjects total who have completed 6 months (achievement of the primary outcome), we will stop study enrollment.

#### *Target and Study Population*

The target population is postmenopausal women with the diagnosis of recurrent UTI as defined by 3 or more symptomatic UTIs within 1 year or 2 UTIs within 6 months. For purposes of this study, we will use the CDC definition of symptomatic UTI as defined above. Our study population will be selected from patients seen at the UCSD Women's Pelvic Medicine clinic as well as those referred from primary care offices at UCSD and those subjects recruited from Researchmatch, Craigslist and approved flyers. In addition, New York University Pelvic Medicine Center will also be recruiting patients from their clinic once IRB approved. A total of 184 new patients were seen with a diagnosis of recurrent UTI between July 2011 to June 2012 at the Women's Pelvic Medicine Clinic.

#### *Inclusion Criteria*

1. Postmenopausal status as defined by amenorrhea for  $\geq 12$  months, OR history of bilateral salpingoophorectomy, OR if the patient has had a hysterectomy defined by menopausal symptoms for  $>1$  year OR age  $>55$
2. Recurrent UTIs (3 or more in the last year or 2 or more in the last 6 months). Patients must have one culture documented UTI, but the others may be documented by urinalysis.
3. Ability to provide informed consent

#### *Exclusion Criteria*

1. Use of any investigational drug or device within thirty days of screening
2. Urologic surgery within the past 3 months of screening or plan for surgery within one year of screening
3. Diagnosis of Interstitial Cystitis/painful bladder syndrome
4. History of urinary tract infections which require the use of IV antibiotics or where only one oral antibiotic is available for treatment, or where the risk of treatment with vaginal estrogen only is deemed unacceptable by the principle investigator secondary to the severity of prior urinary tract infections
5. Known etiology of infection such as, but not limited to: kidney or bladder stones, enterovaginal/vesical fistula, fecal incontinence, intermittent catheterization, indwelling catheter, poorly controlled diabetes
6. Urothelial cancer
7. Actively treated estrogen sensitive tumor (breast or endometrial cancer)

8. Undiagnosed vaginal bleeding
9. Inability to use a vaginal ring (secondary to advanced prolapse or shortened vaginal length)
10. Any medical reason the investigator deems incompatible with treatment with vaginal estrogen
11. Prolapse requiring pessary use

*Deferral Criteria*

1. Undiagnosed hematuria – may enroll after malignancy is ruled out
2. Use of a progestin containing intrauterine device or use of any vaginal androgens, estrogens or progestins within 3 months of enrollment – may enroll after wash out
3. Use of drugs/supplements known to prevent UTIs (ie cranberry products, prophylactic antibiotics, methenamine hippurate) 1 month prior to enrollment – may enroll after wash out if still meets inclusion criteria.

History of estrogen sensitive tumor (breast or endometrial cancer) – requires approval by the subject's primary oncologist or primary care physician

## **11. RECRUITMENT**

The subjects will be recruited from those patients referred to the Women's Pelvic Medicine clinic at UCSD, Thornton campus. Patients are frequently referred to this clinic by primary care physicians when they have repeated UTIs. We will also send out an email to primary care physicians to inform them of the study and post flyers in primary care offices. We will also place an advertisement on Craigslist (see separate document) and we will use ResearchMatch for recruitment (please see separate document for recruitment message).

In addition, we will perform a search of the EPIC system to identify patients with the CPT code diagnosis of recurrent UTI and will contact their primary care physicians to inform them that their patient may be eligible for the study, allowing the primary care physicians to contact their own patients. This presents minimal risk to the patients as the diagnosis of recurrent urinary tract infection carries no stigma and their own physician would contact them about the study should they qualify. There will be no direct contact between the patients and the study staff, just between the study staff and the patients' physicians. We are requesting a waiver of consent for recruitment purposes as a consent form would be the only document linking these patients to the study and would therefore subject them to more risk than the waiver of consent as there is a risk of breach of confidentiality by having the consent document. Because of the large number of patients seen in the UCSD Health System, it would not be practical to try to consent them all to look at their charts for the diagnosis of recurrent urinary tract infection.

We are also requesting a partial waiver of HIPAA authorization. We will request a list of medical record numbers and names of patients with a diagnosis of recurrent urinary tract infections from EPIC. In addition, we will ask for the names of these patient's listed primary care providers. This list will be sent electronically over encrypted mail and will be downloaded onto a secure password protected computer. The primary care physicians will then be sent an email with the name of the patient (again over secure, encrypted email) along with the already approved text informing them about the study, letting them know that their patient may qualify. As soon as these emails are sent out, we will destroy the electronic document. We anticipate this process will take about one week. Again, because of the large number of patients seen in the UCSD Health System, it would not be practical to try to obtain HIPAA authorization to look at their charts for the diagnosis of recurrent urinary tract infection. In addition, this could not be done without the use of PHI as we need to inform the primary care physicians the names and medical record numbers of the patients so that they can contact them should they feel it is appropriate. The contacted patients may greatly benefit from receiving potential treatment for their recurrent urinary tract infections through this study. The privacy risk to these patients is minimal given that only EPIC and study staff will see the list and this part of recruitment will be complete and the list destroyed within a week. Amendment was submitted in July 2013 to add recruitment flyers to UCSD primary care and gynecology clinics.

Subjects will also be recruited at the NYU Pelvic Medicine Center where four collaborative board certified Female Pelvic Medicine and Reconstructive Surgery attendings see their patients (similar to the Women's Pelvic Medicine clinic at UCSD). Only deidentified data will be shared between the principal investigators at the sites.

## **12. INFORMED CONSENT**

Women with recurrent UTI will be introduced to the study opportunity and referred to the physician investigator to be counseled about risks and benefits of enrollment in the study. Patients are typically approached for study participation in the context of their clinic visit and thus consent and study procedures are performed in a private setting as their clinic visit would be. The physician/investigator will explain in detail about the risks and benefits associated with participation in this study. Patients will specifically be consented to randomization to a vaginal ring or one of two vaginal preparations. We will also request that they sign a separate authorization for the use of personal health information as this research is subject to HIPAA privacy rule provisions. Patients who are recruited from outside institutions must provide documentation of UTIs at their recruitment visit and must sign an authorization for the transfer of urine culture and urinalysis results from their healthcare center.

## **13. ALTERNATIVES TO STUDY PARTICIPATION**

The patient may receive vaginal estrogen by prescription. Other therapies in the prevention of recurrent UTI include antibiotic prophylaxis, either postcoital or daily dosing. They may also use cranberry, such as the FDA approved drug Elura, or cranberry supplements along with probiotics. Alternatively, they may take methenamine hippurate daily which is a bactericidal turning urine to formaldehyde and ammonia. Notably, none of these alternative approaches have proven more effective than vaginal estrogen.

The risks associated with specimen collection are minimal and mostly related to inconvenience of providing a urine specimen and discomfort associated with a pelvic examination, however most of these subjects will be having a pelvic examination as part of their clinical care or with placement of the vaginal estrogen ring. Subjects may opt out of having specimens collected at any time.

## **15. RISK MANAGEMENT PROCEDURES AND ADEQUACY OF RESOURCES**

### *Monitoring Plans for Safety*

Data safety and monitoring for adverse events will be overseen by a committee composed of the PI, the study statistician and research mentor. The study staff will conduct monthly telephone interviews with the subjects during the first 3 months of the study to ascertain any adverse events in the treatment arms. The subjects will then be encouraged to call should they experience any adverse reactions. The PI will be notified of any adverse events, which will be reviewed on a case-by-case basis. Any serious adverse events requiring hospitalization and/or surgical intervention will be reported to the institutional IRB within 24 hours of identification of the event. Data will be reviewed on a quarterly basis to assess for completeness, accuracy, or any trends that may require alteration of study protocol, including number of UTIs in each subject. Any errors, omissions or adverse events will be brought to the attention of the PI.

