
The open label portion of the study will start at month 6. All of those women using placebo cream will be allowed to choose a vaginal estrogen preparation to use for the remainder of the study (ring or cream). Those women initially randomized to vaginal estrogen will be allowed to choose which vaginal estrogen preparation they want to continue with. The rationale behind an open label portion of the study is an incentive to participate. Vaginal estrogen is available to patients via prescription, as an off label indication, but coverage for this therapy can be limited and treatment costly (up to \$300 per prescription refill). The open label portion of the study should provide incentive for women to enroll when the study drug is already available, as will modest reimbursement for study visits. We will also be able to compare the rates of UTI in those women who received placebo initially to their rate of UTI on drug.

Eligible women will be consented and block randomized using preset, opaque and sealed envelopes. These cards will either say “study drug 1, 2 or 3” and will be placed in numbered envelopes in a random order and selected by study staff and dispensed to the subject. These drugs will be stored in a locked cabinet in the Female Pelvic Medicine clinic. After the subject receives her study drug, she will receive administration instructions. If the assigned treatment is a ring, the subject will have it placed by the provider, if it is a cream, the cream will be weighed at baseline and she will be shown how to place it vaginally herself and instructed on bringing the remaining study drug to each 3 month visit for weighing.

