**Methodology**  
*Details of the Intervention*

Women will be randomized to one of the two vaginal estrogen arms or placebo in a 1:1:2 fashion. For those randomized to the ring, the ring will be placed by the provider in 3 month intervals at their visits. Subjects randomized to cream arm will receive 0.5g (0.312 mg) conjugated estrogen vaginal cream per vagina at bedtime two times per week. The placebo cream will be administered in a similar fashion. These cream tubes will be weighed at baseline and again at the every 3 month office visits to assess adherence. They will also be given diaries to keep track of their medication administration. Subjects will be called once a month for the first 3 months by study personnel to assess for adverse events as well as UTI symptoms. After the first 3 months, a relationship will be established with study personnel and the participants will be encouraged to call with symptoms.

Written quality of life questionnaires will be administered at baseline, at the end of randomization or 6 months and at drop out (if possible) or 12 months. The questionnaires include the OAB-SAT-q, MESA, UDI-6, FSFI and PSQ, GPI and EPI rating scales and are previously validated questionnaires referenced above in *Overall Design* [26-31]. These will assess global QOL, as well as irritative bladder symptoms and sexual function. We will also collect baseline data with respect to medical history and concomitant pelvic medicine diagnoses.

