### ***Safety and Toxicity Measures***

If subjects in any arm develop 3 UTIs in the 6 month treatment period, they will be unblinded. If on placebo, they will be provided active study drug as would have been done at the 6 month visit or if they are on study drug, they will be treated according to the provider's clinical practice and their outcomes recorded for the remainder of the study. Six month outcome assessments will be administered early to capture QOL data for the secondary analyses. We will also be monitoring for adverse events monthly with phone calls for the first 3 months, specifically querying symptoms of pain, bleeding or abnormal discharge which would prompt evaluation for relatedness to study participation. Events related to participation will not be billed to insurance, however, any events which are part of routine clinical care (ie. UTI or other pelvic floor disorder treatment such as urinary incontinence) will be billed according to standard clinical care. After that subjects will be encouraged to call with any adverse reactions. Attribution of these events to study participation will be assigned by the investigator and reported to the IRB according to local policy.

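### The solicited adverse-event calls are tied to the first 3 months of the study, so women who move from placebo to estrogen at month 6 get none of them on estrogen

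*Combined protocol and SAP*

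**What the plan says.** Three places in the combined protocol and SAP set the schedule, and they agree.

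- Section 9, Methodology (Details of the Intervention): "Subjects will be called once a month for the first 3 months by study personnel to assess for adverse events as well as UTI symptoms".
- Section 9, Safety and Toxicity Measures, describes "monitoring for adverse events monthly with phone calls for the first 3 months, specifically querying symptoms of pain, bleeding or abnormal discharge".
- Section 15, Monitoring Plans for Safety, fixes the reference point as the study: "monthly telephone interviews with the subjects during the first 3 months of the study to ascertain any adverse events". It continues: "The subjects will then be encouraged to call should they experience any adverse reactions".

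The switch comes later. In section 9, Overall Design: "The open label portion of the study will start at month 6". On who starts estrogen then: "All of those women using placebo cream will be allowed to choose a vaginal estrogen preparation to use for the remainder of the study". The allocation, under Methodology, is: "Women will be randomized to one of the two vaginal estrogen arms or placebo in a 1:1:2 fashion". Safety and Toxicity Measures also lets a placebo woman move to active drug before month 6 if she has three UTIs.

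No section restarts the calls at month 6 or ties them to first use of active drug. Visits at months 9 and 12 appear in section 20. The 3-monthly visits are described for ring exchange and weighing of cream tubes, and questionnaires are due at month 12. No adverse-event query is stated for the 9- or 12-month visit.

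**The concern.** The calls are the plan's only stated means of asking women about adverse events. The symptoms they target (pain, bleeding, discharge) overlap with reactions that section 14 lists for vaginal estrogen, such as application-site reaction, bleeding or spotting, and changes in cervical secretions. For the half of the sample randomised to placebo, all three calls are spent on a lubricant with no active ingredient. When these women first use estrogen, the plan relies on them to volunteer a problem.

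Two things are at stake. First, adverse events after first estrogen use are collected by two methods, solicited in one half of the women and volunteered in the other, and nothing tells the analyst to keep the two apart. Second, the same calls ask about UTI symptoms. The plan will compare UTI rates on and off drug within the placebo women, and the solicited contact falls only in the off-drug period. If calls bring out symptoms that would otherwise go unreported, that difference favours estrogen.

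**Working it through.** **Inputs.** Total 48, 24 per group, 20 per group at the end of the randomised period, 20% attrition (section 9, Sample Size Consideration). Allocation 1:1:2 (section 9, Methodology). Three monthly calls in study months 1 to 3 (sections 9 and 15). Estrogen from month 6 for placebo women (section 9, Overall Design). Visits at months 3, 6, 9 and 12 (section 20).

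**Step 1: the plan's own sample size.** With rates of 63% and 16% and two-sided alpha 0.05, exact enumeration gives Fisher's test 82.3% power at 20 per group, so the stated 80% is met (19 per group already gives 81.6%). The inflation 20 × 1.2 = 24 per group gives the stated 48.

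**Step 2: how many women are concerned.**
- Placebo share: 2 / (1 + 1 + 2) = 0.5, and 0.5 × 48 = 24 randomised.
- Expected at month 6: the plan's target is 20 per group; 24 × 0.8 = 19.2 agrees. Section 10 stops enrollment at 40 women who have completed 6 months, and 40 × 2/4 = 20.

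**Step 3: scheduled calls after first estrogen use.**

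| Woman | Estrogen starts | Calls on estrogen | Next scheduled contact after the calls end or estrogen starts |
|---|---|---|---|
| Randomised to ring or cream | Month 0 | 3 | 3- and 6-month visits |
| Placebo, switches at month 6 | Month 6 | 0 | 9-month visit |
| Placebo, switches early after three UTIs | Before month 6 | 0, or a remaining call if before month 3 | 3- or 6-month visit |

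**Step 4: what the gap could cost (illustration only).** The documents give no incidence, so I assume a range. I also assume that every reaction is found in called women and none in uncalled women, which makes the loss an upper bound. The chance of at least one case in n women at incidence p is 1 − (1 − p)^n. Compare n = 24 (randomised to estrogen) with n = 24 + 20 = 44 (adding the women expected to switch).

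| Assumed incidence | n = 24 | n = 44 |
|---|---|---|
| 2% | 1 − 0.98^24 = 38% | 1 − 0.98^44 = 59% |
| 5% | 1 − 0.95^24 = 71% | 1 − 0.95^44 = 90% |
| 10% | 1 − 0.90^24 = 92% | 1 − 0.90^44 = 99% |

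**Step 5: the size of a remedy.** Three calls × 20 women = 60; at most 3 × 24 = 72.

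**The case against.** The best defence is that little in the planned analysis depends on these calls. All arms get the same three calls in months 1 to 3, so the randomised comparison of estrogen with placebo is symmetric. The gap lies in the open-label phase, which the plan presents mainly as an incentive to take part. That stands, and it limits the point.

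A reader might infer that the plan pools adverse events, because Overall Design combines outcomes after the switch with the 6-month measures of women first randomised to estrogen. The documents do not support this. The text speaks of secondary outcomes, which are UTI rates, quality of life, satisfaction and adherence; adverse events are not named, and Data Analysis plans no adverse-event analysis. The concern is about any summary that is made, not about one already planned.

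A reader might also infer that every woman who switches goes without calls or visits until month 9. This is not so for early switchers, as the working shows. Nor may the illustration be read as the expected loss: volunteered reports remain open, and ring users are seen for exchange, so the true loss is smaller and cannot be estimated from the documents. Quarterly data review does not fill the gap, since it examines what has been recorded and elicits nothing new.

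The plan does give a reason for stopping the calls: by then women will have a relationship with study staff and will be encouraged to call. It does not say that the calls were placed early to catch reactions to a new product, so that purpose should not be attributed to it. A good relationship may help reporting, but volunteered reports are still not equivalent to answers to a direct question.

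**Conclusion.** The gap is real and follows from the text alone. A woman who starts estrogen at month 6 has 0 scheduled adverse-event calls on it, against 3 for a woman randomised to it. This concerns 24 women as randomised and about 20 as expected at the switch under 20% attrition. Any summary of estrogen adverse events across both sets is liable to understate them. The on-versus-off-drug UTI comparison in placebo women carries the same imbalance in contact, of a size the documents do not allow one to estimate. Neither the primary outcome nor the randomised 6-month safety comparison is touched. This is a cheap improvement to safety capture and reporting, not a flaw in the main result. The detection percentages depend on the assumed incidence and on zero capture without calls.

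**What to change.** In all three places that state the schedule (section 9 Methodology, section 9 Safety and Toxicity Measures, and section 15 Monitoring Plans for Safety), add that women who move from placebo receive the same three monthly calls, with the same questions on adverse events and UTI symptoms, counted from first estrogen use. This wording also covers early switchers. Add a sentence to Data Analysis that adverse events are reported separately for solicited and volunteered periods.

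The cost is about 60 short calls, at most 72, by staff who already make them. Section 8 reports enrollment complete, so the calls can help only women who have not yet switched or have only recently done so. Separate reporting remains possible for everyone. No dose, treatment rule or primary analysis changes.
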